8.4 PK Analysis Set

According to protocol Amendment 3, the Pharmacokinetic (PK) Analysis Set comprises all randomized subjects who receive at least 1 partial dose and provide at least 1 pre-dose assessment at any study visit that is sufficient to derive plasma concentration of insulin glargine, M1, or M2. Subjects in the PK analysis set will be grouped according to treatment they actually received (defined in Section 7.1).

9. Interim Analyses

There are no planned interim analyses for this study.

10. Data Review

10.1 Data Handling and Transfer

All of the data will come from the PRA Health Sciences data management group in SAS® dataset format (SAS version 9.4 or later), and will be converted to Study Data Tabulation Model (SDTM) version 1.4 using SDTM Implementation Guide (SDTMIG) Version 3.2 following the standard Clinical Data Interchange Standard Consortium (CDISC) conventions. Analysis datasets will be created using SAS® and following CDISC Analysis Data Model (ADaM, version 2.1, Implementation Guide 1.1) Standards.

Medical history and AEs will be coded using MedDRA version 22.0 to assign a system organ class (SOC) and preferred term to each event. Please refer to the Data Management Plan for details.

The following vendors will be providing data:

- PDH: Abbott CGM Data.
- Arcinova: PK data
- Bioclinica: Randomization assignments (contains unblinding information)
 - True randomization assignments will not be loaded into SAS until the time of unblinding for the final analysis.
- Eurofins: Central Laboratory
- WuXi: Immunogenicity

10.2 Data Screening

Beyond the data screening built into the PRA Data Management Plan, the PRA programming of analysis datasets, tables, figures, and listings (TFL) provides additional data screening. Presumed data issues will be output into SAS logs and sent to Data Management.

11.2 Subject Disposition

The following information will be summarized for subject disposition in the FAS:

- Number and percentage of subjects in each analysis set
- Number of subjects screened and a breakdown of screen fail reasons
- Number and percentage of subjects randomized in each site
- Number and percentage of subjects randomized by country
- Number and percentage of subjects who completed the comparative portion (Visits 2-9) of the study, together with the number and percentage of subjects who withdrew from the study prematurely and a breakdown of the corresponding reasons for withdrawal by discontinuation category as recorded in the End of Study CRF page.
- Time from first dose of IP to early treatment discontinuation (also as a Kaplan-Meier plot)
- Number and percentages of subjects completed the study, and reasons for discontinuation collected on the CRF End of study page will be summarized for the FAS, SS, and the PPS.

For subject discontinuation where the reason is recorded as 'Subject withdrawal' or 'Other' in the CRF, additional details could be captured in the clinical trial management system (CTMS) and may be summarized manually and discussed in the clinical study report.

A listing of subjects' randomization numbers, and their actual versus randomized treatment group for all the subjects in the FAS will be provided.

11.3 Important Protocol Deviations

Per PRA processes, protocol deviations data will be entered into the CTMS, in accordance with the Protocol Deviation Guidance Document. The study team and the sponsor will conduct on-going reviews of the deviation data from CTMS, without regard to treatment assignment in accordance with the Blinding Plan. The per protocol analysis sets determined by types of important protocol deviation must be finalized at the data review meeting (or earlier), prior to database lock.

Based on the protocol deviations data entered into CTMS, the important protocol deviations thought to potentially impact the statistical analyses or subject safety will be listed and tabulated using incidence and percentages by deviation type and randomized treatment group in the FAS. Important protocol deviations are defined in the protocol deviation guidance document. The last approved version of protocol deviation guidance will be finalized before the database lock.

1) Immunogenicity-Interfering Important Protocol Deviations (IIIPD)

Important Protocol Deviations are subdivided into those that are thought to interfere with immunogenicity and those that do not. These immunogenicity-interfering important protocol deviations (IIIPD) are listed explicitly in Appendix 4 Immunogenic- and Efficacy-Interfering Important Protocol Deviations and will be used to identify those subjects that are excluded from the Per Protocol Analysis Set 2 (See Section 8.3). This study population will be used in a sensitivity analysis defined in Section 11.6.1.3.

2) Efficacy-Interfering Important Protocol Deviations (EIIPD)

Important Protocol Deviations are also classified into those that are thought to interfere with HbA1c and those that do not. These efficacy-interfering important protocol deviations (EIIPD) are listed explicitly in Appendix 4 and will be used to identify those subjects that are excluded from the Per Protocol Analysis Set 3 (See Section 8.3). This study population will be used in a sensitivity analysis defined in Section 11.7.1.3.

A manual summary of subjects with one or more defective IP pens will be provided and discussed in the clinical study report based on information collected outside of the clinical database. This manual summary will include subject ID, site, investigator name, product quality issue reported, and site / clinical research associate comments.

11.6 Immunogenicity Analyses

All Immunogenicity analysis will be performed using the SS based on all treated subjects.

11.6.1 Primary Endpoint

11.6.1.1 Incidence of Treatment-Induced Anti-Insulin Antibodies

Incidence of treatment-induced AIA is defined as subjects develop newly confirmed positive AIA or have important (4-fold) increase in AIA titer up to visit Week 26. The objective of the primary immunogenicity analysis will be to evaluate equivalence of Gan & Lee Insulin Glargine Injection to Lantus® by comparing the limits of the 90% confidence interval (CI) of country-adjusted difference in proportions of treatment-induced AIA development to the specified margins (-margin, +margin) where the margin is dependent on the unadjusted treatment-induced AIA rate in Lantus® and is defined in Section 5.1, Table 3.

The estimand of interest is the country-adjusted difference in treatment-induced AIA rates regardless if all subjects tolerate or adhere to study treatment or receive other insulin treatments. Intercurrent events will be handled according to the treatment policy strategy. Treatment Policy strategy is defined as the strategy that considers "The occurrence of the intercurrent event is irrelevant: the value for the variable of interest is used regardless of whether or not the intercurrent event occurs" (See ICH E9 R1 addendum). All AIA data collected, scheduled and unscheduled, will be considered for the analysis, even if collected after the occurrence of intercurrent events of (1) discontinuing study treatment, (2) returning to initial treatment and/or (3) initiating a new treatment.

Any treatment-induced AIA after baseline and up to visit Week 26 will have the subject count as treatment-induced AIA for the primary endpoint. The visit window (defined in Section 7.1) will only be limited to include assessment within 210 days from the first dose.

Missing data will be handled as described in Section 11.6.1.2. The SS will be used for the primary analysis.

The number and percentage of subjects in each treatment group who develop treatment-induced AIA as defined in Section 7.2 after baseline and up to visit Week 26 (upper limit of the visit window) will be evaluated using a logistic regression model adjusted by country (CNTRY) estimating the country-adjusted difference in proportions along with the corresponding 90% confidence interval (CI).

Equivalence in difference in proportion δ between Gan & Lee Insulin Glargine Injection (π_1) and Lantus® (π_2) will be tested by comparing the limits of the 90% CI for treatment-induced AIA development with the following null hypothesis:

$$H_0: (\pi_1 - \pi_2) \leq -\delta_0 \text{ or } (\pi_1 - \pi_2) \geq \delta_0$$

Against the alternative hypothesis of:

$$H_1: -\delta_0 < (\pi_1 - \pi_2) < \delta_0$$

where δ_0 is the margin dependent on the observed unadjusted treatment-induced AIA rate in Lantus® (π_2) and is defined in Section 5.1, Table 3.

To evaluate equivalence of Gan & Lee Insulin Glargine Injection to Lantus® the calculated 90% CI has to be entirely contained with the interval $(-\delta_0, \delta_0)$.

A sample SAS code fragment is provided below for reference:

Category	Sample Availability	Imputation	Likely Scenarios
		
 Subject will be counted as 'NOT developing a treatment-induced AIA' if both Week 12 and Week 26 results are negative. 	
4	Any positive results from unscheduled (or out of window) AIA sample(s) during the Treatment Period	
 Positive result from unscheduled AIA sample will be treated the same way as the Week 12/26 samples when baseline result is present. Positive result from unscheduled AIA sample will render the subject as 'developing a treatment-induced AIA' if baseline sample is missing. 	
 Sample collection out of the allowable sample collection window. Sample collection due to other protocol deviations.

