## **8.7 Primary and Secondary Endpoints**

### **8.7.1 Primary Endpoint**

- The percentage of subjects in each treatment group who develop treatment-induced AIA, defined as newly confirmed positive AIA development or important (at least a 4-fold) increase in titers after baseline and up to visit Week 26

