### 9.1 Visit 1: Screening: from Day -14 Through Day -1

At the screening visit, subjects will provide informed consent and will be evaluated for eligibility to participate in the study. After the subject signs the ICF, the following information will be collected or procedures performed:

- Eligibility screening
- Adverse events
- Medical history (including diabetes mellitus and thyroid disease history)
- Prior and concomitant medications (including insulin)
- Vital signs, height, body weight, and BMI
- 12-lead ECG
- Physical examination
- Venous blood samples will be collected for the following tests:
  - Routine hematology and chemistry testing including free T4 and TSH (See [Section 10.5](#) for details)
  - FBG test
  - HbA1c
  - AIA (blood should be collected before the subject administers the regular insulin dose)
- Urine samples will be collected for urinalysis and, for women of childbearing potential, a urine pregnancy test
- A capillary blood glucometer, test strips, and other supplies will be issued and the Investigator or designee will provide instruction and conduct training on how to use the glucometer
- The Investigator or designee will apply a CGM sensor and issue an 8-day Mealtime & Insulin Dose Record, and will instruct the subject about the purpose of the CGM, the need to continue performing glucose self-testing with the glucometer, care of the sensor, and how to complete the Mealtime & Insulin Dose Record (subjects will be instructed to bring the record back to their next visit)
- Subjects will also receive a Hypoglycemic Events Record in which they will record information about any hypoglycemic events during their participation in the study
- During the 2-week period between the screening and randomization visits, subjects will have their basal insulin doses optimized as described in [Section 8.5.8](#).

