### 12.4 Randomization

Subjects will be randomized in a 1:1 ratio to Gan & Lee Insulin Glargine Injection or Lantus® treatment. Subject randomization will be stratified by country.

Registration and randomization will take place using a centralized IXRS. At registration, the IXRS will assign a unique subject identification number that will be used on all of that subject's eCRFs and serious adverse event report forms.

The study is not blinded. However, to avoid the introduction of operational bias into final study results and to increase the interpretability and reliability of the data, certain roles of the Sponsor and study team will be blinded. Details will be provided in the Data Blinding and

Documentation of Aggregate Data Dissemination Plan (hereafter referred to as the Blinding Plan).

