**Table 5: Imputation Rules for Missing Data in the Primary Immunogenicity Analysis**

	Baseline a	Visit Week 12	Visit Week 26	Result/Imputation Rule
1.	x	x	x	No imputation.
2.	x	x	o	Subject will be counted as developing a treatment-induced AIA, impute visit Week 26 as positive result
3.	x	o	x	Subject will be counted as developing a treatment-induced AIA, impute visit Week 12 as positive result
4.	x	o	o	Subject will be counted as developing a treatment-induced AIA, impute visit Week 12 and visit Week 26 as positive result
5.	o	x	x	Subject will be counted as developing a treatment-induced AIA if visit Week 12, visit Week 26, or unscheduled assays up to visit Week 26 indicate positive result; otherwise, subject will be counted as not developing a treatment-induced AIA (all assays up to visit Week 26 are negative).
6.	o	x	o	Subject will be counted as developing a treatment-induced AIA, impute visit Week 26 as positive result
7.	o	o	x	Subject will be counted as developing a treatment-induced AIA, impute visit Week 12 as positive result
8.	o	o	o	Subject will be counted as developing a treatment-induced AIA, impute visit Week 12 and visit Week 26 as positive result

AIA = anti-insulin antibodies; o = AIA data missing, x = AIA data not missing.

a No imputation will be performed for missing baseline values.

Additional sensitivity analyses on the imputation, which explore the limitation(s) of the data or assumption(s) of the primary analysis being evaluated in each sensitivity analysis and how the analysis addresses each, will also be discussed in the SAP.

Missing data will be imputed for the HbA1c analysis. The robustness of the imputation will be explored via sensitivity analyses using multiple imputation and including a tipping point analysis. Full details of the multiple imputation procedure will be presented in the SAP.

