6.3 Other Secondary Endpoints

6.3.1 Immunogenicity

- The percentage of subjects in each treatment group with negative AIA at baseline who develop confirmed positive AIA after baseline and up to visit Week 26
- The percentage of subjects in each treatment group with confirmed positive AIA at baseline and at least a 4-fold increase in titers after baseline and up to visit Week 26
- The mean change from baseline in each treatment group in AIA titers after baseline and up to visit Week 26. Though not specified in the protocol, this analysis is planned for the subset of subjects with confirmed positive AIA at baseline.
- The percentage of subjects in each treatment group with confirmed positive AIA after baseline and up to visit Week 26 who develop any anti-insulin neutralizing antibodies after baseline and up to visit Week 26
- The percentage of subjects in each treatment group with confirmed positive AIA after baseline and up to visit Week 26. This summary is planned to include all subject regardless subject's status of AIA at baseline.

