The 90% CI will be estimated using a pattern mixture model that uses multiple imputation (MI) analyzed using Analysis of Covariance (ANCOVA) with treatment and stratification factor of country (CNTRY) included as fixed effects and baseline HbA1c included as a covariate. Separately in each treatment group, the imputation will use outcomes in subjects who discontinued treatment prior to Week 26 but returned to provide a visit Week 26 HbA1c sample to impute outcomes in subjects without actual visit Week 26 recorded results under the MNAR assumption. Limits of the imputed value will use the minimum of HbA1c values and the maximum of all HbA1c values assessed, and rounded to the nearest integer. These values are found in the database to be minimum as 5 and the maximum as 13. No imputation will be performed for missing baseline HbA1c. Equivalence will be assessed based on the 90% CI; no p-values will be computed. Change from baseline in HbA1c between Gan & Lee Insulin Glargine Injection and Lantus® will be considered equivalent if the 90% CI is within the margins (-0.4%, 0.4%).

For EMA submission, non-inferiority in change from baseline in HbA1c between Gan & Lee Insulin Glargine Injection and Lantus® will be tested using the following null hypothesis:

$$H_0: (\mu_1 - \mu_2) \geq 0.4$$

Against the alternative hypothesis of:

$$H_1: (\mu_1 - \mu_2) < 0.4$$

with a 1-sided $\alpha=0.025$.

In addition, the same non-inferiority test with a margin of 0.3% will be performed.

The 95% CI will be estimated using a pattern mixture model that uses MI analyzed using ANCOVA with treatment and stratification factor of country (CNTRY) included as fixed effects and baseline HbA1c included as a covariate. Separately in each treatment group, the imputation will use outcomes in subjects who discontinued treatment prior to Week 26 but returned to provide a visit Week 26 HbA1c sample (labeled as the unscheduled) to impute outcomes in subjects without actual visit Week 26 recorded results under the MNAR assumption. No imputation will be performed for missing baseline HbA1c.

Analysis of HbA1c will follow a hierarchical testing strategy: first, non-inferiority will be tested using a margin of 0.4% and only if this test is significant, then non-inferiority will be tested using a margin of 0.3%.

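### The primary AIA model adjusts for country only; adding baseline AIA status, already collected before randomisation, could narrow the 90% CI at almost no cost

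*SAP*

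**What the plan says.** SAP 11.6.1.1 states that the proportion with treatment-induced AIA "will be evaluated using a logistic regression model adjusted by country (CNTRY) estimating the country-adjusted difference in proportions", with a 90% CI compared against a margin that depends on the unadjusted Lantus rate. The target is worded to match: "The estimand of interest is the country-adjusted difference in treatment-induced AIA rates".

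The endpoint (Protocol 8.7.1) is "newly confirmed positive AIA development or important (at least a 4-fold) increase in titers after baseline". The secondary endpoints split it into two paths. Subjects negative at baseline qualify by becoming confirmed positive. The other path is for subjects "with confirmed positive AIA at baseline and at least a 4-fold increase in titers after baseline" (SAP 6.3.1).

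The baseline sample is drawn at screening, before randomisation. Protocol 9.1 lists, among the blood tests, "AIA (blood should be collected before the subject administers the regular insulin dose". Protocol 12.4 says "Subject randomization will be stratified by country" and names no other factor.

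For HbA1c, by contrast, the model has treatment and the "stratification factor of country (CNTRY) included as fixed effects and baseline HbA1c included as a covariate" (SAP 11.7.1).

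**The concern.** Baseline AIA status is a natural candidate predictor of the primary outcome, because the two baseline groups must meet different criteria to count as events. Nothing in the design balances it between arms. The SAP uses the baseline value for HbA1c but not for the primary endpoint, and the available text gives no reason.

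If event rates differ by baseline status, in either direction, leaving the covariate out keeps avoidable variance in the risk difference, including the part due to chance imbalance in the baseline-positive share. The cost is a wider 90% CI and a lower chance of showing equivalence when the products are equivalent. The sample size allows for no drop-outs, while SAP 5.1 reports more early discontinuation than expected, so precision is worth having.

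**Working it through.** **Inputs from the documents.** n = 275 per arm, 1:1; TOST at one-sided α = 0.05 (a 90% CI); worked example with event rate p = 0.30, margin 0.12 and true difference 0 (Protocol 12.2, 12.4; SAP 5.1).

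**Inputs assumed.** Baseline-positive share w = 5-50%; gap d between the two baseline groups' event rates = 0 to 30 points, with the overall rate held at 30%. The documents give neither figure.

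**The plan's own figure.** SE = √(2p(1−p)/n) = √(0.42/275) = 0.0391. The CI half-width is 1.645 × 0.0391 = 6.43 points. Power = 2Φ(0.12/0.0391 − 1.645) − 1 = 84.6%, against the stated 85% or so.

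**Effect of the covariate.** The variance of the marginal risk difference is multiplied by 1 − R², where R² = w(1−w)d²/[p(1−p)]. The sign of d does not matter. At w = 0.50 and d = 0.30, R² = 0.25 × 0.09/0.21 = 10.7%.

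| Gap d | R² (w = 10-50%) | Half-width, points | Power |
|---|---|---|---|
| 0 | 0% | 6.43 | 84.6% |
| 10 points | 0.4-1.2% | 6.41-6.39 | 84.8-85.1% |
| 20 points | 1.7-4.8% | 6.37-6.27 | 85.4-86.7% |
| 30 points | 3.9-10.7% | 6.30-6.07 | 86.3-89.1% |

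The share could be low, because Protocol 8.4.2 excludes subjects with previously documented AIA; a positive screening result is not itself listed as an exclusion. At w = 5% and d = 30 points, power is 85.5%.

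**Dilution by imputation.** Protocol Table 5 counts subjects with missing post-baseline samples as events. If a share m of both groups is imputed this way, p′ = m + (1−m) × 0.30 and d′ = (1−m)d, with the margin interpolated from Protocol Table 4. For d = 30 points and w = 10-50%:

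- m = 10%: rate 37%, margin 12.6 points, power 85.7-87.8% against 84.4% without the covariate.
- m = 20%: rate 44%, margin 13.0 points, power 85.3-86.9% against 84.3%.

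**Simulation check.** Settings: 275 per arm, five equal countries (assumed), randomisation stratified by country, standardised risk difference with delta-method 90% CI, 30% baseline positive, 3,000 replicates.

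- Equal rates: SE ratio (adjusted to unadjusted) 1.000; the two powers differ by 0.3 points, which is noise.
- 16% against 36%: SE ratio 0.980; power goes from 84.9% to 86.8%.
- 9% against 39%: SE ratio 0.954; power goes from 85.0% to 88.9%.

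Adjusted coverage was 89.0-90.2%. A separate simulation, with the margin taken from the observed reference rate, gave the same width reductions for these three cases (0%, 2.0% and 4.6%). Its coverage was 88-91% for both models.

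**Scale of chance imbalance.** With w = 30%, the between-arm difference in baseline-positive share has SD √(2 × 0.3 × 0.7/275) = 3.9 points. With a 30-point gap, a 1-SD imbalance moves the unadjusted difference by 0.30 × 3.9 = 1.2 points, a tenth of the margin. This is part of the variance reduction above, not an additional benefit.

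**The case against.** **No defect is shown.** Adjusting for the sole stratification factor is coherent, the interval is valid and the power is as stated. This stands: the point concerns efficiency only.

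**The gain is assumed and may be small.** A 10-point gap adds at most 0.5 points of power, and larger gains need a wide gap and a sizeable baseline-positive group. This also stands. The case for acting is that the change costs almost nothing, not that the gain is assured.

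**Sparse strata could destabilise the model.** With 5% baseline positive and rates of 31.5% and 1.5%, about 28 subjects would yield 0.4 expected events, and the stratum would contain none about 65% of the time. This was tested with 5% baseline positive and a rate of 1.5% or 0% in that stratum. The standardised estimate kept a stable SE, coverage was 88-90%, and power was no lower than with country alone. The overall confirmed-positive endpoint (SAP 11.6.2.5) could have the mirror-image problem, a stratum that is nearly all events; no separate calculation was made for it.

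**It is late.** The logistic method was itself adopted after regulatory review, the SAP is dated 27 May 2021 and the trial is open-label. A further change to the primary model needs justification and possibly renewed review. However, SAP 10.1 keeps true assignments out of the analysis system until final unblinding, and the covariate precedes randomisation.

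**It may be handled elsewhere.** The primary SAS code, SAP 7.2 and the later sensitivity analyses are not in the text available, so a supportive baseline-adjusted analysis cannot be ruled out. The primary model statement is nevertheless explicit.

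**Conclusion.** The concern holds as a recommended improvement. The primary model omits a pre-randomisation variable that determines the event definition each subject faces, so its 90% CI may be wider than it needs to be.

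There is no gain and no measurable loss if event rates are equal across baseline groups. The upper end of the range examined, a 30-point gap with half the subjects baseline positive, is equivalent to 550/(1 − 0.107) ≈ 616 subjects instead of 550. Low baseline-positive prevalence and imputation of missing samples as events both reduce the benefit. Different event definitions make unequal rates plausible, but the documents do not show them, so confidence in the size of the gain is only moderate.

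**What to change.** Before treatment assignments are loaded, amend SAP 11.6.1.1 as follows:

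- Add baseline AIA status (confirmed positive versus not) to the logistic model with country. Estimate the marginal risk difference by standardisation, with a delta-method 90% CI.
- For this covariate only, code missing baseline with baseline-negative. This keeps every Safety Analysis Set subject in the model. It also follows Protocol Table 5, row 5, where a subject with missing baseline counts as an event "if visit Week 12, visit Week 26, or unscheduled assays up to visit Week 26 indicate positive result". A separate missing level would be sparse and could be all events (rows 6-8).
- Reword the estimand as the marginal risk difference adjusted for country and baseline AIA status.
- Keep the margin tied to the unadjusted Lantus rate, and keep the country-only model as supportive.
- Apply the same covariate in SAP 11.6.2.5, and state there and for the primary model what is done if the fit does not converge.

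The cost is one model term, a coding rule and a few sentences of SAP text, plus any review that a change to the primary model requires. No new data are needed, and neither the risk-difference scale nor the margin rule changes.
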